active-listening, and role plays, using BFT approaches. Lastly, it will use tips from Motivational Interviewing for eliciting SP encouragement for PE participation, creating a tailored plan for SPs to support PE, and assisting SPs in follow-up telephone calls. The training team is highly seasoned in educating providers in these methods. The training will be video-taped for use in training future providers (e.g., due to provider attrition during the course of the study).

5.1C. Standard PE.

Providers will deliver PE consistent with the standard of care, with a flexible end date as they typically would in routine practice and will divide Session 2 into 2a and 2b. VA PE trainings encourage extending the therapy as needed, routinely resulting in a range of 8 to 15 sessions. Posttreatment assessments will be scheduled to coincide with when Veterans complete treatment to allow for this flexible end date. If participants are still in treatment at 16 weeks post-session 1, the posttreatment assessment will be delayed to allow them to get through as much of the treatment as possible prior to assessment. If the Veteran never attends session 1, their posttreatment will be scheduled 16 post-first missed appointment for session 1.

Family attendance will not be solicited by providers in standard PE. If a SP contacts a provider, the provider will proceed as he/she would in his/her routine practice, consistent with our design emphasis on real-world care. Quantity and quality of provider-SP contact will be measured by weekly provider report. We anticipate risk for cross-over effects from SPs reaching out to providers is minimal as considerable effort is required by SPs to gain access to Veterans' providers (i.e., Veterans must request and sign a Release of Information). Additionally, while we did not capture who initiated the provider-SP contacts reported among 17% of SPs within Project HomeFront, qualitative interviews suggest these contacts are typically initiated by providers. In qualitative interviews, SPs were enthusiastic about being involved in Veterans' care, but few SPs had considered reaching out to Veterans' providers.

Table 2. Content Added for Family Supported PE	
PE#	Task
1	
 • Eliciting benefits of further SP attendance • Brief discussion of how SPs can help in PE
2a	
 • Brainstorm how SPs encourage/discourage PE adherence and approaching trauma-reminders

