Our study sites have robust telemedicine programs that provide PE by telemedicine. Study sites will follow all procedures and regulations that are currently in place at their VA hospital and surrounding CBOCs to ensure services provided to Veterans are safe and accurate. Additionally, all practitioners treating patients using telemedicine will be qualified to deliver the level of consultation, care, and treatment involved.

5.1F. Defining Drop Outs

Participants could, without notice, stop coming to treatment, and then contact their providers several months later to request to re-initiate treatment. This could lead to vastly different periods of time that some participants are in treatment (watering down treatment effects and potentially artificially influencing study findings) and could also pose administrative problems if they would be unable to complete posttreatment or follow-up assessment during the period of funding for the project. Additionally, at some point such a break in treatment would become long enough such that starting treatment again would be equivalent to starting treatment over (e.g., like a new course of care). Consequently, any unanticipated break in treatment for longer than 6 consecutive weeks will trigger an official 'end' to their treatment period. Participants will remain in the study protocol (i.e., receive all study assessments and not removed from the study). They will be assessed at 16 weeks post session 1 for their posttreatment survey and interview. If they request to re-enter care, they will be referred to the clinic to intiate a new course of care with the clinic, outside of the study.

5.1G. Provider Monitoring and Fidelity Assessment.

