For RCT phase, structured clinical interviews will take place at Baseline (week 0) and posttest (within 4 weeks of final session). Self reports/surveys will take place at Baseline (during week 0) and at posttreatment (during final session). For drop out Veteran participants, posttest surveys will be completed 16 weeks post-session 1 and the posttreatment clinical assessment will be done within 4 weeks of that posttest survey. For late treatment completers (i.e., treatment takes more than 16 weeks), all posttest surveys and post clinical interviews will be delayed but will be done no later than 24 weeks post-session 1.

For the IC phase, weekly surveys will be given for the first 2 weeks of treatment (session 2a, and 2b). For the RCT phase, weekly surveys will be given during weeks 2, 4, 5, 6, 8, 10 and 12 of treatment. For participants, the weekly surveys during week 2 and 8 will be lengthier and more thorough. All structured interviews (CAPS-5³ and SCID-5-CT)¹² will be administered by trained and supervised assessors who are blinded to condition. Assessors will be trained and supervised weekly by [name], a licensed clinical psychologist with expertise in conducting structured diagnostic clinical interviews and assessing and intervening with patients experiencing mental health crises. For mailed assessments, we will use CCDOR's well-established modified-Dillman protocol with repeated mailings and an incentive (incentive schedule described below).⁶ For surveys of Veterans with PTSD, our team's response rates

have ranged from 55% to 85%. Given the short interval between assessments, we will include a telephone call reminder and an offer telephone administration to optimize response rates.⁶

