6.0 Reporting

We will follow the VA Central IRB Table of Reporting Requirements for all issues that must be reported (i.e. summary of adverse events, unexpected problems and any actions or changes with respect to the protocol).

Adverse events (AE) include any untoward medical occurrence in a patient or clinical investigation subject administered an intervention and which does not necessarily have a causal relationship with this treatment. We will collect the following safety information (adverse events) that occurred within 7 days leading up to the final assessment.

1. Suicide attempts
2. Hospitalizations for mental health
3. Episodes of family violence

Therapists will be instructed to notify study staff immediately when such events occur during treatment delivery. Staff will report directly to the local site PI regarding any events. Counselors will also meet regularly by phone for case consultation with a study investigator, where the occurrence of any of these events will be further discussed and tracked. Questions regarding the occurrence of each of these three events will be included in posttreatment assessments. Data obtained from participants will be reviewed for safety concerns. In the case of problems, the staff will discuss this with the appropriate site PI.

Of note, survey reports of IPV on posttreatment and follow-up surveys will be reported when respondents endorse items consistent with severe violence. This includes the following: (1) hit my partner with a fist or something hard, (2) kicked my partner, (3) slammed my partner against something, (4) beat my partner, (5) burned my partner on purpose, (6) tried to hurt my partner by choking or suffocating him/her, or (7) used a knife or gun on my partner. Examples of serious adverse effects, according to the FDA, include death, life-threatening adverse events, suicide attempts, and hospitalization. Consequently, endorsement of items 6 or 7 will be considered a SAE. Given the population, some incidents of severe IPV are expected. Reports of severe IPV on baseline surveys are part of our exclusionary criteria (see inclusions/exclusions). Thus, severe IPV in reported in baseline surveys will not be reported as adverse events.

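### Section 6.0 states one adverse-event recall period, 7 days before an undefined final assessment, which conflicts with its other sentences and leaves attempts and admissions after therapy ends uncertainly or not covered

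*Combined protocol and SAP*

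**What the plan says.** Section 6.0 (Reporting) lists three events to be collected as safety information: suicide attempts, mental health hospitalizations and episodes of family violence. The only recall period it gives is this: "We will collect the following safety information (adverse events) that occurred within 7 days leading up to the final assessment". The term *final assessment* is not defined.

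The same section describes three other routes:

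- Therapist report: "Therapists will be instructed to notify study staff immediately when such events occur during treatment delivery". Regular consultation calls add to this.
- Posttreatment questions: "Questions regarding the occurrence of each of these three events will be included in posttreatment assessments". No recall period is attached.
- Later surveys, for violence only: "survey reports of IPV on posttreatment and follow-up surveys will be reported when respondents endorse items consistent with severe violence".

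Assessment timing is set elsewhere. Completers fill in the posttreatment survey at their last session and are interviewed within 4 weeks of it (5.5A.2). Dropouts stay in the study and keep receiving assessments (5.1F). For them, "posttest surveys will be completed 16 weeks post-session 1 and the posttreatment clinical assessment will be done within 4 weeks of that posttest survey" (5.5A.2). For Veterans who never start, 5.1C says: "If the Veteran never attends session 1, their posttreatment will be scheduled 16 post-first missed appointment for session 1". The number has no unit. Both arms get a further survey 3 months after posttreatment (5.1I.2, 5.5A.3).

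Section 5.1K.1 closes a therapy case on completion, when the Veteran says he or she has quit, or once outreach after missed sessions is exhausted. Section 5.1F ends the treatment period after an unplanned break exceeding 6 weeks.

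**The concern.** The sentences in 6.0 do not describe one coherent collection rule. A 7-day look-back suits events recorded at a single visit, but the section also expects reports throughout treatment and asks about events at posttreatment with no look-back stated. A reader cannot tell whether the final assessment is the posttreatment survey, the posttreatment interview or the 3-month survey.

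The ambiguity matters most once the therapist is no longer in contact. From then on, a suicide attempt or psychiatric admission is learned of through an enquiry to the Veteran, or because it is volunteered or surfaces through a risk screen. Section 6.0 itself gives suicide attempts and hospitalization as examples of serious events, and the 5-business-day reporting clock starts only when the study PI learns of one. If the enquiry covers 7 days, a serious event in the preceding weeks may never start that clock. The Veterans most exposed are those who left therapy early or never began. For the period between posttreatment and the 3-month survey, everyone is exposed.

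Family violence is less affected, because severe-violence items on the posttreatment and follow-up surveys are reported as events.

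**Working it through.** The plan states no figure for this point, so there is nothing to reproduce. The check is calendar arithmetic, conditional on the posttreatment questions using the 7-day (1-week) window.

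**Inputs**

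- Window: 1 week (6.0).
- Dropout survey: week 16 after session 1 (5.1F, 5.5A.2).
- Latest dropout interview: week 16 + 4 = 20 (5.5A.2). Section 5.1F places both survey and interview at week 16.
- Never-starter assessment: 16 after the first missed appointment (5.1C), assumed to mean weeks.
- Follow-up survey: 3 months after posttreatment, taken as 91 days = 13 weeks.
- Closure of the therapy case: no interval is given in 5.1K.1, so two range ends are used. The early end is closure at the last session, as when a Veteran announces quitting. The late end is 6 weeks after the last session, borrowed from the break rule in 5.1F. Outreach may end at any point between them.
- Last session in week 3, 5 or 8: illustrative, because the documents give no dropout timing.

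**Formula**

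Uncovered weeks = assessment week − 1 − closure week.

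**Dropouts**

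| Last session | Closure week | Before survey, week 16 | Before latest interview, week 20 |
|---|---|---|---|
| Week 3 | 9 to 3 | 16−1−9 = 6 to 16−1−3 = 12 | 20−1−9 = 10 to 20−1−3 = 16 |
| Week 5 | 11 to 5 | 16−1−11 = 4 to 16−1−5 = 10 | 20−1−11 = 8 to 20−1−5 = 14 |
| Week 8 | 14 to 8 | 16−1−14 = 1 to 16−1−8 = 7 | 20−1−14 = 5 to 20−1−8 = 11 |

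**Never-starters:** 16−1−6 = 9 to 16−1−0 = 15 weeks, counted from the first missed appointment.

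**Completers:** none before the survey, which is given at the last session. If the events are asked only at the interview, at most 4−1 = 3 weeks.

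**Posttreatment to 3-month survey, all Veterans:** 13 of about 13 weeks if *final assessment* means posttreatment, since 6.0 names only violence for the later survey. If it means the 3-month survey, 13−1 = 12 weeks. This result does not depend on when a case closes.

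**Do other routes fill these weeks?**

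- Therapist reports and consultation calls rest on what the therapist knows during treatment.
- Returned surveys are screened for suicidal ideation and risk-related free text (5.1K.1), not for past attempts or admissions. If weekly surveys continue after dropout and weeks run from session 1, a week-5 dropout is still sent them in weeks 6, 8, 10 and 12, then nothing until week 16.
- The C-SSRS asks about suicidal acts in the past 3 months, but is given only when triggered, and it does not ask about admissions. A survey response above threshold goes first to the Veteran's VA mental health provider. Use of the suicide protocol is logged as an adverse event.
- The call log and annual DSMB reporting (5.1M), and Central IRB reporting (6.0), act on information already received.

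None of these commits the study to asking every Veteran about the two events.

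**The case against.** The strongest reply is that the gap before posttreatment rests on instruments that are not shown. The posttreatment questions may ask about the whole study period, in which case that gap disappears. This stands, and the finding is conditional for that reason. It does not rescue 6.0: on that reading the 7-day sentence is wrong and should go. Likewise, silence about these items on the 3-month survey does not prove they are absent, only that the plan does not commit to them.

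A second reply is that closure at the last session exaggerates the gap for Veterans who drift away, whose cases stay open during outreach. This also stands, which is why ranges are given. The short end may still be generous, since a therapist who cannot reach a Veteran may not hear of an event either.

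Third, 6.0 describes adverse events in a subject who has been administered an intervention, so never-starters may fall outside its definition. That is fair. The section should say whether they are covered.

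Fourth, reporting itself has no 7-day limit, and Veterans' medical records are already read for attendance (5.5A.1). Both are true. But reporting follows knowledge, and nothing assigns records to finding these events after enrolment.

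A reader might infer more than the documents support:

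- That nothing is collected outside the 7 days. The therapist and screening routes contradict this.
- That a treatment comparison is biased. Section 5.6 plans no between-arm harms analysis, so unequal detection by arm is only a possibility.
- That a number of affected Veterans follows from the roughly 35% dropout cited in 2.0. Without the timing of dropout or an event rate, it does not.

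**Conclusion.** Section 6.0 is internally inconsistent on when safety events are collected, and its final assessment is undefined. That much is certain from the text. What follows depends on the recall used in the posttreatment questions. With 7-day recall, attempts and admissions after case closure are not routinely asked about for 1 to 12 weeks before the week-16 survey, or 5 to 16 weeks before the latest interview, across last sessions in weeks 3 to 8. For never-starters the figure is about 9 to 15 weeks, and for completers at most 3. With longer recall, the 7-day sentence misstates the plan. On either reading, no question on these two events is stated for the 3-month survey, leaving 12 to 13 of about 13 weeks uncovered.

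The figures assume that treatment delivery ends at case closure, a definition which 5.1K.1 gives for reviewing survey reports of partner violence. They also assume that closure falls between the last session and 6 weeks after it, that the unit missing in 5.1C is weeks, and that 3 months is 91 days. The partial routes reduce the consequence for suicide risk more than for hospitalization. This is a weakness in safety ascertainment that should be corrected. It does not undermine the efficacy analyses.

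**What to change.** In 6.0:

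1. Replace the 7-day window with two collection periods: randomisation to posttreatment, and posttreatment to the 3-month survey.
2. Ask about suicide attempts and mental health hospitalizations over those periods on the existing posttreatment and 3-month assessments, with identical wording in both arms and including dropouts.
3. State that never-starters are covered, and reconcile this with the section's definition of an adverse event.
4. List therapist-reported events separately from those obtained by these questions.
5. Define *final assessment* or remove the term, and supply the missing unit in 5.1C.

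If the posttreatment items already ask over the full period, only the text of 6.0, the unit in 5.1C and the 3-month survey need to change.

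The cost is a Central IRB amendment, a revised recall period on existing questions, and two items on an existing survey. No visit is added. Longer recall brings some recall error and slightly more events to process. Non-responders remain unreached; the plan itself assumes 20% missing posttreatment PCL scores (5.6A2). The current protocol is version 16, dated September 2021, so a change may come mid-trial and make ascertainment differ between earlier and later participants. Record which version each Veteran received, and report events by version.

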Reports of risk on study surveys. All surveys will be screened within 2 business days of receipt by study staff. This will ensure that surveys are typically screened within 48 hours of receipt by a study staff, barring holidays and weekends (e.g., staff has until Tuesday to screen a survey received on Friday). Staff will read any text written into the survey for any risk-related concerns, as well as review responses to the adapted Linehan BRTC SI screen items that directly assess suicidal ideation. Staff will be carefully trained about the importance of opening surveys promptly and entering receipt of each survey into the study tracking application. Auditing will be performed quarterly to ensure that the staff member reviewed the participants responses on Linehan BRTC SI screen items and intervened appropriately when the final item response was greater than "5".

If any psychiatric emergency is reported on surveys (i.e., expression of risk for suicide or homicide) or a response of greater than "5" on Linehan BRTC SI screen items, the participant's VA Mental Health Provider will be notified using phone, skype, and pager. If the participant does not have a VA Mental Health Provider or their VA Mental Health Provider is unavailable (we are not able to reach the provider within the same business day), a study designated MH provider would do the necessary outreach. There are a number of licensed MH providers on the study team. Some are clinically privileged and others are not clinically privileged (e.g., Research Service employees). When providers are not privileged, we propose they will utilize the C-SSRS screener as outlined in the study protocol (see "Suicide Management Protocol"). When providers are privileged, we propose they use either the C-SSRS screener protocol or a more stringent approach to suicide risk assessment that is consistent with VA guidelines.

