IPV reports on surveys. Baseline, weekly, and posttreatment surveys ask about intimate partner violence (IPV). IPV reports are not routinely considered psychiatric emergencies that warrant breaching participants' confidentiality. Additionally, reaching out to all those who endorse IPV may have unintended negative consequences. Reaching out when uninvited to ask IPV victims to further discuss their IPV may be distressing and bring up traumatic memories. The outreach may be unwelcome, perceived as intrusive, and discourage future reporting. Discussing violence over the phone may also place the victim at risk to be overheard by the abuser, other loved ones, or children in the home. Consequently, a list of resources will be included with baseline, posttreatment, and follow-up surveys, including for IPV. Letters accompanying surveys will encourage respondents to contact study staff if they would like to discuss any of their survey responses. We will rely on participants to contact study staff if they wish to discuss their IPV experiences further. If participants are excluded due to IPV, the staff member notifying the reporter of their exclusion will offer local and national resources for IPV.

When the IPV reporter is actively engaged in psychotherapy in our study (i.e., veterans who are actively participating in PE and loved ones are actively participating in PE2), the reporter has an ongoing relationship with their study provider. In this circumstance, the reporter has the

reasonable expectation that the provider is reviewing their surveys and may ask them more about it. Thus, when a participant is actively engaged in psychotherapy in our study, providers will review IPV survey responses and intervene as clinically indicated, keeping the safety of the reporter of paramount concern. Providers will not breach the reporter's confidentiality unless they have the reporter's verbal permission or are concerned they must do so to prevent imminent harm.

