Veterans will be considered 'actively engaged in psychotherapy in our study' when their study therapist has not officially closed their therapy case. Cases are closed when the veteran has completed their course of PE, when the veteran tells their therapist they have quit PE, or when providers have exhausted outreach attempts to a veteran who has missed a scheduled session(s). SPs in the PE2 condition are considered 'actively engaged in psychotherapy in our study' when their veteran is actively engaged in psychotherapy in our study. SPs in the Standard PE condition are never considered 'actively engaged in psychotherapy in our study.'

Managing risk from CBOCs and in-home video telehealth sessions. Due to the nature and distance between the Veteran and telemental health provider incurred in telemedicine practice, additional measures will be taken to ensure patient safety. These procedures will be in place during all telemedicine sessions:

- a. Study providers will follow the guidelines detailed in the 2017 Department of Veteran Affairs National Telemental Health Supplement and the 2012 Telemental Health Suicide Prevention and Emergency Care manual.
- b. Providers will use VA approved electronic communication methods
- c. All study providers will follow their site's local telemental health policies and emergency procedures at each facility and clinic.
- d. Providers will always adhere to established face-to-face assessment protocols.
- e. Telemental health provider will have detailed contact information from the patient with particular attention to who could be contacted in the event of an emergency. All emergency contact information, local police phone numbers and local emergency room contact information should be readily retrievable during all sessions.
- f. Providers will use the National Telehealth Help Desk when necessary: [name].

Additional manners to manage risk from CBOCs.

- a. For all telemental health sessions at CBOC locations, a CBOC staff person will be available to assist Veteran should the need arise.
- b. CBOC staff will be available by telephone for the remote telemedicine study provider should they need to emergently contact an on-site VA staff.
- c. If a patient becomes suicidal, homicidal, psychotic, or agitated, the Telehealth provider will ask for assistance from the CBOC staff who would help in deescalating the patient and/or initiating commitment.

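### Weekly partner-violence answers fall outside the survey adverse event rule, and during treatment they have an assigned reviewer for both dyad members only in the family supported arm

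*Combined protocol and SAP*

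**What the plan says.** **Which surveys ask.** Under IPV reports on surveys, 5.1K.1 states: "Baseline, weekly, and posttreatment surveys ask about intimate partner violence (IPV"). In the RCT phase, 5.1I.2 and 5.5A.2 schedule weekly surveys for Veterans and SPs in weeks 2, 4, 5, 6, 8, 10 and 12. The week 2 and week 8 forms are longer.

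**Which answers become adverse events.** Section 6.0 says that "survey reports of IPV on posttreatment and follow-up surveys will be reported when respondents endorse items consistent with severe violence". It lists seven severe items and classes the last two as serious. Baseline reports are left out because severe violence at baseline is an exclusion criterion. Weekly reports are not mentioned.

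**Who reviews IPV answers during treatment.** According to 5.1K.1, "when a participant is actively engaged in psychotherapy in our study, providers will review IPV survey responses and intervene as clinically indicated". Eligibility for that review depends on arm. In the family supported arm, which that section calls PE2, "SPs in the PE2 condition are considered 'actively engaged in psychotherapy in our study' when their veteran is actively engaged in psychotherapy in our study". In the other arm, "SPs in the Standard PE condition are never considered 'actively engaged in psychotherapy in our study".

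**What staff screening covers.** 5.1K.1 also says: "All surveys will be screened within 2 business days of receipt by study staff". The content of that screening is then set out: "Staff will read any text written into the survey for any risk-related concerns, as well as review responses to the adapted Linehan BRTC SI screen". IPV items are not named, and the quarterly audit concerns the suicide items only.

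**Other routes in 6.0.** Therapists in either arm must tell staff at once about family violence during treatment, and it is tracked on consultation calls. Posttreatment assessments ask about all three listed safety events. One general sentence says that participant data are reviewed for safety. The same section limits adverse event collection to the week before the final assessment.

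**The concern.** Family violence is one of only three safety events the trial collects, and it bears directly on an intervention that brings the SP into treatment. A reader of the results will want to compare it between arms. A fair comparison needs the same chance of an event being seen and recorded in each arm.

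The written rules do not give that. While treatment is active, two people's IPV answers are assigned for review in a family supported dyad, and one person's in a standard dyad. With equal true rates, this would tend to make family supported PE look worse. Separately, in either arm, violence disclosed only on a weekly form has no stated path into the survey-based adverse event count.

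**Working it through.** The plan gives no IPV rate and no expected event count, so there is no figure to reproduce. The check traces the routes by arm and then counts forms.

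**1. Routes from a disclosure to a record**

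| Route | Standard PE | Family supported PE |
|---|---|---|
| Veteran's weekly IPV items reviewed by provider (5.1K.1) | Yes, while the case is open | Yes, while the case is open |
| SP's weekly IPV items reviewed by provider (5.1K.1) | Never | Yes, while the Veteran's case is open |
| Staff screening of weekly surveys (5.1K.1) | Written-in text and suicide items | Same |
| Weekly IPV answer named in the survey adverse event rule (6.0) | No | No |
| Posttreatment and follow-up severe items named in that rule (6.0) | Yes | Yes |
| Therapist notification (6.0) | Yes, but SP attendance is not solicited (5.1C) | Yes, and the therapist meets the SP in Session 1, usually in 2a and 2b, and in two calls (5.1D) |

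The second and last rows differ by arm, both in the direction of more ascertainment in the family supported arm. The gap may also widen over time. Provider review stops when a case closes, including when the Veteran quits, so if attendance is better in the family supported arm, as Aim 1 hypothesizes, review lasts longer there.

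**2. Forms affected**

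Inputs: 78 dyads per arm (5.1), 7 weekly surveys per person (5.1I.2), and one posttreatment and one 3-month survey per person (5.5A).

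- Reporters with an assigned reviewer during treatment: 1 per standard dyad, 2 per family supported dyad.
- Standard-arm SP weekly forms with no assigned reviewer of the closed IPV items: 78 × 7 = 546. All weekly forms: 156 × 2 × 7 = 2,184. Share: 546 / 2,184 = 25%.
- If IPV items are only on the week 2 and 8 forms: 78 × 2 = 156.
- Scheduled post-baseline surveys outside the survey adverse event rule, per dyad: 14 weekly against 4 later, so 14 / 18 = 78%. With weeks 2 and 8 only, counting the forms that would carry IPV items: 4 / (4 + 4) = 50%.

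These are upper counts of scheduled forms. SPs may be relatives or friends, so items worded about a partner may not apply to all of them.

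**3. Would the posttreatment questions recover it?**

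The collection window in 6.0 is 7 days. That is 1/11 = 9.1% of an 11-week course, 1/16 = 6.3% of 16 weeks, and 1/24 = 4.2% if the assessment is at the 24-week limit in 5.5A.2. Read literally, violence at week 4 falls outside it. The window also sits poorly with the in-treatment notification and follow-up survey rules in the same section.

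**4. Why 2 reporters to 1 is not a detection ratio**

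Assume, for illustration only, equal true rates and that each reviewed reporter independently discloses with probability q. Detection is q in standard PE and 1 − (1 − q)² in family supported PE, a ratio of 2 − q.

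| q (assumed) | Standard | Family supported | Ratio |
|---|---|---|---|
| 0.2 | 20% | 36% | 1.8 |
| 0.3 | 30% | 51% | 1.7 |
| 0.5 | 50% | 75% | 1.5 |
| 0.7 | 70% | 91% | 1.3 |

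Positive correlation between the two members' reports would bring the ratio closer to 1. The documents supply no value of q, so the table shows direction, not size.

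**The case against.** **Content of the weekly forms.** A reader might infer that severe violence is asked about every week, so that a standard-arm SP could report a serious event at week 4 unseen. The documents do not establish this. They say only that weekly surveys ask about IPV. The outline of weekly content in 5.1I.2 does not list IPV, the forms are not in the document, and 6.0 mentions the severe items only for baseline, posttreatment and follow-up surveys. If no severe items are on weekly forms, adding those forms to the rule captures nothing. This objection stands, and it is why the form counts are upper limits.

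**Other routes.** It would also be too strong to say that nobody reads these surveys or that the events are counted nowhere. Staff open every survey and read written-in text. Therapists notify in both arms, and the standard-arm Veteran's own answers are reviewed. Section 6.0 also has its posttreatment questions and general safety-review sentence. These routes limit the harm without removing the asymmetry. Therapist contact with SPs is itself uneven by arm, and the general sentence names no reader, form or timing.

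**No planned comparison.** Neither the monitoring plan in 5.1M nor the analysis section 5.6B specifies a safety comparison by arm, so it cannot be said that a biased comparison is planned. That stands. The concern is with the data any such comparison would use.

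**Protection of reporters.** 5.1K.1 argues at length against uninvited outreach and limits when providers may disclose a report. Logging an answer already received requires no outreach, so that argument does not defeat a recording rule. But the text does not say how the disclosure limit fits with therapist notification, so the path from provider review to an adverse event is unsettled.

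**Conclusion.** The point holds as a defect in the safety recording rules, worth fixing but not critical. Two things are plain in the text. The survey adverse event rule omits weekly surveys without a reason. Assigned review of IPV answers during treatment covers both dyad members in one arm and only the Veteran in the other. Up to 546 scheduled standard-arm SP forms (156 under the narrower assumption) have no assigned reviewer of the closed IPV items.

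Unequal ascertainment by arm is a supported risk. With equal true rates it would make family supported PE look worse. Its size cannot be computed from the documents, because disclosure rates, true rates and the content of the weekly forms are not given. It would be wrong to infer a two-to-one detection ratio, or that 78% of events are missed: those figures count reporters and scheduled forms, not events. The primary outcome, session attendance, and its analysis are unaffected.

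**What to change.** In 6.0, apply one recording rule for the listed severe IPV items to weekly surveys (wherever those items appear), posttreatment surveys and follow-up surveys, for Veterans and SPs in both arms. State which weekly forms carry the items. Have the staff who already screen each survey check and log those items in the same way in both arms.

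Report events by source and by arm. Base any between-arm comparison of severe IPV on the survey source alone, and list provider-notified events separately.

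The sponsor needs to reconcile this rule with two existing passages: the seven-day collection window in 6.0, and the confidentiality and outreach text in 5.1K.1. The proposal concerns recording only; how the study team responds to a report is outside it.

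The cost is a short edit to 6.0 and to the screening log, a few more items to check on forms already opened within two business days, and more adverse and serious adverse event reports to the central IRB.
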